1.6.5 AAT Target Level for Proposed Dose in Treatment of GVHD

It is hypothesized that during acute GVHD, AAT may attenuate inflammation, inhibit development of T-memory cells and enhance Tregs and protect against damage and down-regulate inflammatory cytokines. The target level of AAT, based on both *in vitro* and clinical data suggest that targeting a level above the upper limit of normal values may provide the optimal regulation of T cells and cytokines to ameliorate GVHD symptoms. This target level of AAT is likely to provide sustained AAT levels, thereby enhancing Tregs and reducing the pro-inflammatory cytokines.

A PK model of 1000 subjects has been used to simulate a variety of AAT doses and dose regimens, with the intent to identify those which result in mean AAT peak level estimates around or above the upper limit of normal, i.e., ≥ 2.5 mg/mL. The simulated concentration–time profiles generated using AATD PK estimates was validated with data in GVHD patients from the literature and multiple doses were modeled.

Based on this simulation, the dose of 120 mg/kg twice weekly for 4 weeks achieved median trough levels above the upper limit of normal (ULN) and provided sufficient separation in median AAT levels when compared with a dose 60 mg/kg twice weekly. In addition, this dosing regimen shows

that > 50% of the simulated GVHD subjects at this dose regimen achieve serum AAT levels above normal physiologic levels almost immediately after initiation of treatment, and levels are maintained throughout the 28-day treatment period. The cumulative weekly dose (240 mg/kg/week) is similar to the dose regimen of 270 mg/kg/week shown to be safe in Marcondes et al trial⁶⁷.

1.6.6 Ruxolitinib for the Treatment of Steroid-Refractory Acute GVHD

The Janus kinase (JAK) and signal transducers and activators of transcription (STAT) signaling pathways play an important role in immune-cell activation and tissue inflammation during acute GVHD. Ruxolitinib is an oral selective inhibitor of JAK1 and JAK2 that reduces the incidence and severity of GVHD *in vivo* while preserving graft-versus-leukemia effects in preclinical models. Recently, ruxolitinib was granted FDA approval in the United States for patients 12 years and older who develop steroid-refractory or dependent acute GVHD grade II-IV based on the results of a prospective phase 2 trial (REACH1). At a protocol-specified dose of 10mg twice daily, 54.9% of the 36 enrolled patients achieved a response on Day 28 without additional therapy. Simultaneously, an open-label, phase 3 trial (based on the same study criteria) was performed outside of the United States with patients randomized to ruxolitinib 10mg twice daily versus best available therapy (BAT). The results on this study were recently published and showed a higher Day 28 and Day 56 response rate in the ruxolitinib arm when compared to BAT (62% vs. 39%; odds ratio, 2.64; 95% C.I. 1.43 to 3.94; P< 0.001) and (40% vs. 22%; odds ratio 2.38; 95% C.I. 1.43 to 3.94; P< 0.001), respectively. Adverse events were not significantly different between the study arms with thrombocytopenia, anemia and CMV infection being most common.

The availability of an FDA-approved agent for patients enrolled onto this trial may affect the frequency and timing of use of next-line therapy. Importantly, while the results of the REACH 1 and 2 trials are encouraging, a majority of patients will not achieve or maintain a response through Day 56 of treatment with ruxolitinib and outcomes remain poor for patients with steroid-refractory acute GVHD. In an effort to improve upon the outcomes seen thus far with ruxolitinib in a steroid-refractory setting, patients that progress or are non-responders on the current trial will have the option to stay on AAT/PTM when next-line therapy with ruxolitinib is initiated. These patients will be followed for secondary endpoints (while being considered a failure for the primary endpoint). Importantly, the wealth of experience with AAT outside of the study indication would suggest that AAT is unlikely to have drug interaction with ruxolitinib nor contribute additional safety concerns.

CHAPTER 2

2 STUDY DESIGN

2.1 Study Overview

This study is a phase III, multicenter, double-blinded, randomized, placebo-controlled trial designed to compare AAT and CS to PTM and CS as first-line therapy for patients with high-risk acute GVHD.

2.2 Hypothesis and Specific Objectives

2.2.1 Primary Hypothesis

The primary hypothesis is that the addition of AAT to standard therapy with CS will improve the Day 28 post-randomization complete response (CR)/partial response (PR) rate in patients with newly diagnosed high-risk acute GVHD.

2.3 Study Objectives

2.3.1 Primary Objective

The primary objective of this trial is to compare the rate of CR and PR on Day 28 post-randomization between AAT and CS versus PTM and CS in patients with high-risk acute GVHD.

2.3.2 Secondary Objectives

1. Evaluate the duration of response at 6- and 12-months post-randomization.
2. Cumulative incidence of non-relapse mortality at 6- and 12-months post-randomization.
3. Overall survival and progression-free survival at 6- and 12-months post-randomization.
4. GVHD-free survival at Day 56 post-randomization.
5. Proportions of CR, very good partial response (VGPR), PR, and treatment failure (TF) at Days 7, 14, 21, 28, 56, and 86 post-randomization.
6. Proportions of CR, very good partial response (VGPR), PR, and treatment failure (TF) at Days 7, 14, 21, 28, 56, and 86 post-randomization for patients who receive ruxolitinib or other second line therapies approved by the protocol Chairs as next-line therapy and remain on AAT/PTM.
7. Incidence of systemic infections to assess safety.
8. Incidence of Adverse Events at 30 days post last dose of drug to assess safety.
9. Incidence of chronic GVHD at 6- and 12-months post-randomization.
10. Incidence of disease relapse at 6- and 12-months post-randomization.

2.3.3 Exploratory Objectives

1. AAT levels in serum at Days 0, 8, 16, 24, 28, and 56 post-treatment initiation.
2. Stool concentrations of AAT at baseline and at Days 8 and 28 post-treatment initiation.

3. Blood ratios of T regulatory to T effector cells (Treg/Teff), Natural Killer (NK) cells and cellular immune subsets at baseline and at Days 16, 28, and 56 post-treatment initiation.
4. Serum levels of inflammatory cytokines and biomarkers at baseline and at Days 8, 28 and 56 post-treatment initiation.
5. Overall and organ-specific response rates comparison based on Minnesota (MN) risk groups (Revised Minnesota High vs Standard) and organ-specific response rates comparison based on biomarker-based risk groups.
6. Corticosteroid dose at baseline, Days 7, 14, 21, 28, 56, 86, 6 months and 12 months post-randomization.
7. CMV reactivation requiring therapy by Day 56 post-randomization.
8. Change in patient-reported outcomes from baseline to Day 28, Day 56, and 6-months post-randomization.
 - a. MD Anderson Symptom Inventory (MDASI)
 - b. Patient-Reported Outcome Measurements Information System (PROMIS)

2.4 Patient Eligibility

Patients meeting the eligibility criteria should be enrolled as soon as possible after the start of CS, but no more than 72 hours afterwards.

2.4.1 Inclusion Criteria

1. Patients experiencing their initial presentation of acute GVHD requiring systemic therapy after allogeneic transplant for any malignant or non-malignant indication.
2. The clinical diagnosis of acute GVHD requiring systemic therapy with CS. Patients can be enrolled with only a clinically established diagnosis. Biopsy of involved organs with acute GVHD is encouraged but is not required and should not delay study entry. Enrollment and randomization include a commitment to continue steroids with PTM or AAT as specified in the protocol, as well as the required follow-up observations. *If, according to institutional practice, the intention to treat is dependent upon biopsy results, the patient should not complete enrollment on the BMT CTN 1705 study until the biopsy results are available.*
3. Acute GVHD must meet one (either A or B) of following clinical features within 72 hours prior to enrollment:

A. High-risk by Refined Minnesota Criteria (any one below):

Single organ involvement

- a. Stage 4 skin
- b. Stage 3-4 lower GI
- c. Stage 1-4 liver

Multiple organ involvement

- a. Stage 1-2 lower GI plus any liver
- b. Stage 2 lower GI plus any skin
- c. Stage 3-4 lower GI plus any liver or skin
- d. Any three organ involvement

OR:**B. Either of the below:**

1. Isolated stage 2 involvement of the lower GI tract
2. Stage 1 lower GI tract disease with skin involvement
4. Acute GVHD developing after allogeneic hematopoietic cell transplantation using any graft or donor source or conditioning intensity.
5. Patients should not have received systemic immune suppressive therapy for treatment of active GVHD except for a maximum of 72 hours of prior CS therapy prior to enrollment. Topical skin and GI CS (such as budesonide and oral beclomethasone dipropionate) are allowed.
6. Patients 12 years of age or older at time of enrollment.
7. Ability to provide written informed consent from patient, parent or legal guardian, and assent if applicable.

2.4.2 Exclusion Criteria

1. Patients with prior exogenous AAT exposure for GVHD prophylaxis.
2. Relapsed, progressing or persistent malignancy
3. Evidence of minimal residual disease (MRD) requiring withdrawal of systemic immune suppression.
4. Patients with acute GVHD developing after administration of a donor lymphocyte infusion (DLI) for relapse / progression of disease. Patients with acute GVHD after planned donor lymphocyte infusion or planned T cell or NK cell add back are eligible.
5. Patients with uncontrolled infections will be excluded. Infections are considered controlled if appropriate therapy has been instituted and, at the time of enrollment, no signs of progression are present. Progression of infection is defined as hemodynamic instability attributable to sepsis, new symptoms, worsening physical signs or radiographic findings attributable to infection. Persisting fever without other signs or symptoms will not be interpreted as progressing infection.
6. A clinical presentation resembling de novo chronic GVHD or overlap syndrome (as defined in APPENDIX C) developing before or present at the time of enrollment.
7. Patients receiving other drugs for the treatment of GVHD. Note, GVHD prophylaxis agents (e.g., calcineurin inhibitors) may be continued at local Investigator's discretion.
8. Patients receiving systemic CS for any indication within 7 days before enrollment, except the following:
 - a. CS administered as premedication for supportive care (such as before transfusion of blood products or before intravenous medications to prevent infusion reactions, fever, etc.).
 - b. If steroid therapy has been administered for treatment of a non-GVHD related condition and tapered to \leq 0.6 mg/kg/day prednisone (0.5 mg/kg/day methylprednisolone) for 7 or more days prior to enrollment.

- c. Treatment of active GVHD with CS is allowed for up to 72 hours prior to enrollment.
- 9. Patients who are pregnant or breastfeeding.
- 10. Females of childbearing potential (FCBP) or males who can get a FCBP pregnant and have sexual contact with FCBP and are unwilling to use 2 effective forms of birth control or abstinence from the start of study drug treatment through 30 days after the last dose of study drug, Effective forms of birth control are listed in APPENDIX D.
- 11. Patients on renal replacement therapy.
- 12. Patients requiring continuous supplemental oxygen (O_2 requirement $> 2L/min$ to maintain peripheral O_2 saturation [SpO_2] $> 90\%$).
- 13. Patients with active hepatic sinusoidal obstructive syndrome (SOS) and/or clinical evidence of impaired hepatic function (ascites or encephalopathy related to liver disease) who in the judgment of the treating physician are not expected to have normalized bilirubin by Day 56 after enrollment.
- 14. Patients with a history of hypersensitivity to AAT or any component of the investigational product or PTM (albumin), including congenitally IgA-deficient patients with antibodies to IgA or PTM.
- 15. Patients unlikely to be adherent to study specific assessments at the transplant center.

2.4.3 Adolescent Population

The protocol was amended (v4.0), after DSMB review and approval, to include patients between the ages of 12 to 17.99 years after 40 adult patients had been enrolled onto the trial and completed the Day 56 follow-up assessment for safety.

2.5 Treatment Plan

2.5.1 Alpha 1 – Antitrypsin (AAT)

2.5.1.1 Drug Information – AAT

AAT is a lyophilized product for IV administration. Each product package contains 1 single-use vial of lyophilized powder and 1 single use vial of sterile water for injection.

AAT will be manufactured by CSL Behring (CSLB) in accordance with International Conference on Harmonisation (ICH) Good Manufacturing Practice (GMP) guidelines and local regulatory requirements.

Information on the preparation and administration of AAT is provided in the Investigational Medicinal Product (IMP) Handling Instructions.

2.5.1.2 Drug Information – PTM

The PTM solution will be a commercial albumin product (5% Alburex) diluted in 5% dextrose to a visual match to reconstituted AAT solution of 50 mg/mL. An unblinded pharmacist or designee will prepare the AAT solution or PTM solution. Once prepared, the solutions are a visual match, allowing the study team to be blinded to the assigned treatment.

Instructions for preparation of PTM by an unblinded pharmacist or designee are presented in the Investigational Medicinal Product Handling Instructions.

2.5.1.3 Packaging and Labeling

The investigational products will be packaged and labeled according to current ICH GMP and Good Clinical Practice (GCP) guidelines, and national legal requirements.

Investigational products will be packaged in an unblinded manner and prepared at the site by an unblinded pharmacist or designee.

2.5.1.4 Supply and Storage

Investigational products will be supplied to the study sites by CSLB or delegate.

AAT must be stored under temperature-controlled and monitored conditions at the predefined temperature range in a secure storage area as specified in the Investigational Medicinal Product Handling Instructions.

PTM must be stored under temperature-controlled conditions between 2-8° C.

2.5.1.5 Drug Accountability and Destruction

1. Investigational products must be used only as directed in the clinical study protocol.
2. The unblinded pharmacist or designee must provide reasons for any discrepancies in drug accountability.
3. All investigational products must be accounted for throughout the study.
4. Records for the delivery of investigational products to the study site, the inventory at the study site, the dispensing and the destruction of investigational product to CSLB / designee must be maintained by the unblinded pharmacist or designee as described in the IMP Handling Instructions. Administration of investigational products is recorded in the electronic case report forms (eCRF).
5. Any unused, partially used, or empty vials of investigational product should be retained, if possible. On-site destruction must be in compliance with applicable local & national regulations and per site's SOPs.
6. All drug accountability records must be stored in the Suvoda Interactive Response Technology system (IRT) and site file and must be readily available for inspection by the unblinded study monitor and / or auditor, and open to regulatory inspection at any time.
7. The Investigator (and/or hospital pharmacist) will ensure that all study drug is stored in a secured area under required storage conditions and is dispensed by qualified staff members. All study drug will be accounted for in the Suvoda IRT system.
8. The Investigator is responsible for maintaining drug accountability records. Drug accountability records will be reviewed during monitoring visits. Study drug must be administered only to patients enrolled in this study as per the protocol.
9. The unblinded study monitor will be allowed at intervals, and upon request during the study, to check unused supplies. Accounting for the use of supplies will be by reference

to each center's record of supplies received, the dispensing records for the total number of patients enrolled at each center and the unused and returned supplies.

10. Further details regarding accountability and destruction of investigational product are provided in the IMP Handling Instructions and the Suvoda IRT Manual.

2.5.1.6 Reconstitution/Preparation of AAT (Zemaira®)/PTM

Details with regard to preparation and distribution of the study drug can be found within the IMP Handling Instructions. AAT/PTM should be administered within 24 hours of preparation.

2.5.1.7 Dose and Administration

The first dose of study drug (AAT/PTM) **must be initiated as soon as possible after enrollment and must be within 12 hours of enrollment**. Each dose of study drug will be 120 mg/kg (actual weight) based on the patient's weight recorded at enrollment. Subsequent doses should be given on Days 4, 8, 12, 16, 20, 24, 28 (Table 2-1). **The patient's weight recorded at enrollment will be used to determine the dose for all infusions** (i.e., dose adjustments for changes in weight during the treatment period will not be made).

Patients that are non-responders or progress will be considered to be steroid-refractory (SR) and may start next-line therapy as described in section 2.5.3.3. Ruxolitinib is recommended for next-line therapy as it is an FDA-approved treatment for SR-GVHD.

Responding patients (CR/PR) at Day 28, compared to maximum GVHD organ staging within 72 hours prior to enrollment, that are receiving study drug alone, or study drug plus ruxolitinib, should continue to receive treatment at a dose of 120 mg/kg (actual weight) on Days 35, 42, 49, and 56 (Table 2-1). Patients who are not in CR/PR at Day 28 will not continue to receive study drug. Responding patients at Day 28 who progress after Day 28 may continue to receive weekly doses through Day 56.

Patients that receive next-line therapy other than ruxolitinib may not continue receiving study drug unless approval is granted by the BMT CTN 1705 Protocol Chairs.

Table 2-1 Study Drug Schedule

	Day											
	0 ¹	4	8	12	16	20	24	28	35	42	49	56
All patients	X	X	X	X	X	X	X	X				
CR/PR (VGPR) patients only									X	X	X	X

¹ Enrollment is Day 0, First dose of study drug must occur within 12 hours after enrollment and may fall on Day 0 or Day 1.

Patients can receive study drug (AAT/PTM) as either an inpatient or outpatient. All subsequent treatments will have a window of \pm 3 days to allow for efficient scheduling of patients for holidays/weekends/etc. Following administration of the first or second dose, adjusting future infusions to accommodate a Monday/Thursday or Tuesday/Friday schedule is encouraged.

Infusion Rate: AAT/ PTM should be administered at a rate not exceeding 0.08 mL/kg body weight/minute. If adverse events occur, the rate should be reduced, or the infusion interrupted until the symptoms subside. The infusion may then be resumed at a rate tolerated by the subject.

Monitoring: Vital signs (temperature, heart rate, blood pressure, respiratory rate) should be recorded at a minimum: pre-infusion, approximately 10 minutes into the infusion and approximately 20 minutes after completion of the infusion. It should be noted that infusion reactions during and following AAT administration have been reported but are rare. These include:

- Uncommon ($\geq 1/1,000$ to $< 1/100$): hypersensitivity reactions (including tachycardia, hypotension, confusion, syncope, oxygen consumption decreased and pharyngeal oedema), flushing, infusion-site reactions (including infusion site hematoma)
- Very rare ($< 1/10,000$): anaphylactic reactions

If anaphylactic or severe anaphylactoid reactions occur, the infusion should be discontinued immediately. Epinephrine and other supportive therapy should be available for the treatment of any acute anaphylactic or anaphylactoid reaction.

2.5.1.8 Dose Interruptions

Study drug (AAT or PTM) may be held at the discretion of the treating physician and resumed at their discretion. Rationale for missed doses should be recorded. Patients that do not receive study medication for 3 consecutive doses or miss 4 doses in total will be removed from further study treatment.

Infections

Patients with severe infections resulting in hemodynamic instability requiring use of vasopressor medication may have study drug held at the discretion of the treating physician.

2.5.1.9 Adverse Events Related to Study Drug (AAT or PTM)

Adverse Events of Study Drug (AAT or PTM)

Patients with a non-hematologic grade 3 or higher adverse event which is not attributable to an anticipated post-transplant event may have their study drug held at the attending physician's discretion. Anticipated post-transplant events include GVHD and chemotherapy toxicities (see Appendix E and Section 2.5.2.2 respectively.). Study drug should be restarted after recovery of related toxicities to grade 2 or lower or identification of an alternative cause for these toxicities.

Observed adverse reactions as identified from clinical studies in AAT-deficient subjects and during post marketing use of AAT can be found in the Investigator Brochure AAT CSL964.

Adverse Events related to PTM (Alburex)

Adverse reactions to albumin 5% are rare, although nausea, fever, chills or urticaria may occasionally occur.

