2.5.1.10 Study Drug Discontinuation Criteria

Patients that progress or are non-responders and receive ruxolitinib as next-line therapy are encouraged to continue study drug (AAT/PTM).

Study drug shall be discontinued and not re-instituted if any one of the following criteria is met:

- Patient does not receive study medication for 3 consecutive doses or 4 doses in total for any reason, including toxicity.
- Patients that receive next-line therapy other than ruxolitinib not approved by the BMT CTN 1705 Protocol Chairs.
- Relapse or progression of underlying malignancy.
- Pregnancy or initiation of breastfeeding during the study; refer to Section 4.4.5.
- Withdrawal of consent from study and/or study drug

The reason for discontinuation of study drug must be documented by the study team. All randomized patients, including those that did not receive any study drug, discontinued study drug and/or failed treatment, are evaluable for all endpoints of the study and should continue with protocol-specific follow-up and data collection unless the patient has specifically withdrawn consent to provide data.

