APPENDIX E ANTICIPATED TOXICITIES

The purpose of this appendix is to outline those AEs that commonly occur in the study population. The following is a list of events that the Sponsor considers to be common toxicities for agents used in HCT conditioning and GVHD prophylaxis regimens. The events listed below require reporting via the Toxicity CRF in Advantage eClinical and **do NOT change the reporting obligations, timelines or prevent the need to report an AE meeting the definition of an SAE.**

If aggregate analysis of these events indicates they occur more frequently with study drug, an expedited safety report may be submitted to regulatory agencies.

Lack of relationship to the investigational product is not automatically assumed; therefore, an assessment is required by the Investigator for any events specified below. The Sponsor will also perform the causality assessment on a case-by-case basis and expedite reporting to regulatory agencies when applicable.

General Disorders

Fever

Immune System Disorders

Allergic reaction

GI Disorders

Mucositis

Nausea

Vomiting

Gastric ulcer

Esophagitis

Pancreatitis

GI perforation

Increased appetite

Anorexia

Renal Disorders

Cystitis noninfective

Acute kidney injury

Chronic kidney injury

Hemorrhagic Disorders

Hemorrhage

Blood & Lymphatic Disorders

Leukocytosis

Anemia

Thrombotic thrombocytopenic

purpura/Thrombotic microangiopathy

Hemolytic Uremic Syndrome

Vascular Disorders

Thromboembolic event

Respiratory Disorders

Hypoxia

Dyspnea

Investigations

Neutrophil count decreased

Platelet count decreased

ALT

AST

Bilirubin

Alkaline phosphatase

Hyperglycemia

Hypokalemia

Weight gain

Cardiac Disorders

Hypotension
Hypertension
Cardiac arrhythmia
Left ventricular systolic dysfunction
Pericardial effusion
Restrictive cardiomyopathy

Nervous System Disorders

Restlessness
Insomnia
Glaucoma
Headache
Somnolence
Seizure

Musculoskeletal Disorders

Myopathy
Tendon rupture
Bone fracture
Avascular necrosis
Osteoporosis
Arthralgia

Skin Disorders

Erythema
Rash acneiform

Endocrine/Metabolic Disorders

Cushingoid
Adrenal insufficiency
Edema

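### No rule in the protocol or SAP bars further study drug after a related anaphylactic or severe anaphylactoid reaction

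*Protocol*

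**What the plan says.** Four consecutive protocol sections bear on dosing after an infusion reaction.

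- **2.5.1.7** has two tiers. For adverse events in general, the infusion is slowed or interrupted, and "The infusion may then be resumed at a rate tolerated by the subject". For the severe tier, "If anaphylactic or severe anaphylactoid reactions occur, the infusion should be discontinued immediately".
- **2.5.1.8** is a general discretion: "Study drug (AAT or PTM) may be held at the discretion of the treating physician and resumed at their discretion". A patient who misses 3 consecutive doses, or 4 in all, comes off study treatment.
- **2.5.1.9** lets the attending physician hold drug for a non-hematologic event of grade 3 or higher, unless it is attributable to an anticipated post-transplant event. It then says: "Study drug should be restarted after recovery of related toxicities to grade 2 or lower or identification of an alternative cause for these toxicities".
- **2.5.1.10** opens its list with "Study drug shall be discontinued and not re-instituted if any one of the following criteria is met". The five criteria are missed doses, unapproved next-line therapy, relapse or progression, pregnancy or breastfeeding, and withdrawal of consent.

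SAP 7.3 has the same structure: anaphylaxis ends an infusion, and a separate five-item list ends treatment.

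**The concern.** The restart sentence asks whether the toxicity has resolved. That suits an event whose danger lies in its persistence. An anaphylactic reaction may well have resolved before the next scheduled dose, and its danger lies in re-exposure. Recovery to grade 2 or lower therefore says little about whether the next dose is safe.

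The protocol already treats this hazard as disqualifying at entry: exclusion 14 in 2.4.2 bars patients with a history of hypersensitivity to AAT or albumin. A reaction observed on study has no matching rule. The protocol does write mandatory stops where it wants them; pregnancy appears both in 2.5.1.10 and in 4.4.5.

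At stake is the safety of a rare patient. The decision on the next dose rests on individual judgment across about 25 centers, with no stated bar to guide it.

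**Working it through.** **Reading the text.** The question is whether any sentence forbids a later dose after a related anaphylactic or severe anaphylactoid reaction.

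1. *2.5.1.7* acts on the current infusion. The severe tier lacks the resumption wording of the milder tier, but neither tier addresses later doses.
2. *2.5.1.8* allows a physician not to resume, without requiring it.
3. *2.5.1.9* may or may not apply. Its hold provision excludes anticipated post-transplant events: "Anticipated post-transplant events include GVHD and chemotherapy toxicities (see Appendix E and Section 2.5.2.2 respectively". Appendix E lists "Allergic reaction", which would take the event outside the rule. Appendix E also states "Lack of relationship to the investigational product is not automatically assumed", and the restart sentence itself concerns related toxicities, which would keep a drug-related reaction inside it. If the rule applies, it favors restart after recovery. If it does not, only 2.5.1.8 remains. Neither reading gives a bar.
4. *2.5.1.10*: none of the five criteria names the event. Toxicity enters only through missed doses. After a reaction to the Day 0 infusion, the third consecutive missed dose is nominally Day 12 (Days 4, 8, 12). A physician can reach a permanent stop that way, but the reaction itself does not trigger it.
5. *Exclusion 14* is an entry criterion.
6. *4.4.4.3* makes an anaphylactic infusion reaction reportable within 24 hours, in time for oversight before the nominal Day 4 dose. It attaches no dosing consequence.

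**Doses at issue.** Table 2-1 has 8 infusions through Day 28 and 4 more for patients in CR/PR at Day 28. After a first-dose reaction, 8 − 1 = 7 remain, or 12 − 1 = 11 for a Day 28 responder.

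**Expected cases.** Section 2.5.1.7 puts anaphylactic reactions below 1/10,000, without saying per patient or per infusion. For 68 AAT patients with no missed doses, infusions number 68 × 8 = 544 (nobody continues) to 68 × 12 = 816 (everyone continues). At the assumed 75% response rate, 51 patients continue: 544 + 51 × 4 = 748. Expected cases are n/10,000, and the chance of at least one is 1 − (1 − 0.0001)^n:

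| Basis | n | Expected cases | Chance of at least one |
|---|---|---|---|
| Per patient | 68 | <0.0068 | <0.68% |
| Per infusion, none continue | 544 | <0.054 | <5.3% |
| Per infusion, 75% continue | 748 | <0.075 | <7.2% |
| Per infusion, all continue | 816 | <0.082 | <7.8% |

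**What cannot be sized.** The documents give no separate rate for severe anaphylactoid reactions and no numeric rate for albumin. Hypersensitivity of any grade is listed below 1/100. On a per-patient basis that caps the AAT arm at 68/100 = 0.68 cases, with the severe share unknown.

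**The case against.** The strongest reply is that this is silence plus clinical discretion, and that few physicians would re-dose after anaphylaxis. Much of that stands.

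- A reader might infer that the protocol directs rechallenge. It does not: the hold is optional, the restart is advisory, and 2.5.1.8 leaves resumption to the physician.
- A reader might take the restart sentence as the provision written for this event. It is a general sentence for grade 3 or higher events. The text specific to anaphylaxis is in 2.5.1.7, which does not point to restart.
- A reader might conclude that the trial has no contraindication anywhere. The documents cannot show that. Section 2.7 makes the IMP Manual a governing conduct document, 2.5.1.1 and 2.5.1.6 refer to the IMP Handling Instructions, and 2.5.1.9 refers to the Investigator Brochure. None is available here.
- Experience is reassuring. Section 1.5.3 reports no infusion reactions in 40 steroid-refractory patients on the same product, though at 60 mg/kg rather than 120 mg/kg. Section 2.4.3 records that 40 adults completed Day 56 safety follow-up before adolescents were admitted.

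What survives is narrower. None of these points supplies a rule against a later dose in the protocol or SAP, and the sentence that may apply tests recovery without an exception.

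**Conclusion.** The gap is real as a matter of text and worth closing as a low-frequency safety fix. In the protocol and SAP, a related anaphylactic or severe anaphylactoid reaction stops the infusion but does not bar the next one.

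Fewer than 0.007 (per patient) to 0.082 (per infusion) cases of anaphylaxis are expected in the AAT arm. This assumes that the listed rate carries over to this population and to 120 mg/kg; the per-infusion figures also assume no missed doses. The conclusion is limited to the two documents, and the IMP Manual and Investigator Brochure should be checked. It does not extend to every grade 3 or higher hypersensitivity reaction: the documents give no rate for that group, and its listed signs include non-specific ones such as tachycardia and hypotension. It has no bearing on the validity of the efficacy analysis.

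**What to change.** 1. Add one criterion to 2.5.1.10, using the terms already in 2.5.1.7: *Anaphylactic or severe anaphylactoid reaction judged related to study drug (AAT or PTM), unless an alternative cause is identified.*
2. Begin the restart sentence in 2.5.1.9 with *Except after such a reaction (see Section 2.5.1.10),*.
3. Repeat the new criterion in SAP 7.3, for consistency only; that section describes compliance and does not govern dosing.

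Section 2.5.1.8 needs no edit, because the permanent-stop list overrides its discretion. Milder reactions stay under the slow-and-resume rule in 2.5.1.7. No unblinding is needed, since the item covers both products.

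The cost is that a rare affected patient loses the remaining doses (7 to 11 after a first-dose reaction); the alternative-cause clause limits this. Relatedness and alternative cause remain site judgments, so some variation between centers will persist. Follow-up continues under 2.5.1.10, SAP Table 16 handles treatment discontinuation by treatment policy, and the sample size does not change.
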